5.5. Analysis Windows

Analysis windows will not be defined in this study. Only the scheduled visits will be included in the analyses. All visits, including unscheduled visits, will be presented in the listings.

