- Unscheduled visits as needed in the event of signs or symptoms of potential hepatic and/or muscular injury or decompensation or if laboratory alerts have been triggered

It is important that the laboratory assessments be completed as required and that the central laboratory be used for assessments whenever possible. In the event that a subject cannot return to the clinic for a scheduled or unscheduled visit, or there is an event that triggers a need for an immediate assessment, the use of a local lab is permissible at the discretion of the Investigator. In these cases, the Investigator will obtain the laboratory results and the laboratory normal ranges.

The process for assessing criteria is presented in Figure 2, and the specific threshold(s) for each laboratory analyte to trigger investigational product interruption are summarized in Table 5.

Figure 2: Management Algorithm for Potential Hepatic and/or Muscular Injury

CK=creatine kinase; INR=international normalized ratio; IP=Investigational Product; PK=pharmacokinetic

Notes: Laboratory assessments include: ALT, ALP, AST, GGT, direct and total bilirubin, INR, and CK.

PK sampling should be conducted within 7 days of IP interruption; close monitoring including physical exams and repeat biochemistry labs should occur as often as deemed appropriate by the Investigator (Table 4).

Table 4: Laboratory Criteria for Monitoring of Potential Hepatic and Muscular Injury for Interruption^a of Investigational Product

Baseline ^b	Treatment Emergent	Liver Signs and Symptoms ^c
Any value	Any hepatic enzyme elevation (TB, ALP, AST, ALT, GGT)	Yes
ALT or AST Normal	ALT or AST ≥ 3 x ULN and TB ≥ 2 x BL	Yes or No
	ALT or AST ≥ 3 x ULN and INR >1.5	Yes or No
	ALT or AST ≥ 5 x ULN and Any TB	Yes or No
ALT or AST Elevated	ALT or AST ≥ 2 x BL and TB ≥ 2 x BL	Yes or No
	ALT or AST ≥ 2 x BL and INR >1.5	Yes or No
	ALT or AST ≥ 3 x BL (or ≥ 300 U/L, whichever occurs first) and Any TB	Yes or No
TB \leq ULN	TB ≥ 2 x BL and $>$ ULN	Yes or No
TB $>$ ULN	TB ≥ 1.5 x BL or ≥ 3.0 mg/dL, whichever occurs first	Yes or No
ALP \leq ULN	ALP ≥ 2 x BL and $>$ ULN	Yes or No
ALP $>$ ULN	ALP ≥ 2 x BL or ≥ 1000 U/L, whichever occurs first	Yes or No
CK	≥ 5 x ULN or ≥ 3 x ULN with symptoms of rhabdomyolysis ^{d,e}	N/A

BL=baseline; CK=creatinine kinase; DILI=drug-induced liver injury; INR=international normalized ratio; IP=investigational product; N/A=not applicable; TB=total bilirubin

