^a Interrupt study drug; Initiate workup of competing etiologies and close monitoring (repeat labs and exam 2-3 times per week), including repeat labs initially.

- Study drug can be restarted after a minimum of 30 days if another etiology is identified, liver enzymes return to baseline, lab abnormalities are determined not to be due to DILI, no symptoms, and approved by the Medical Monitor and Investigator.
- If study drug is restarted after 30 days, repeat labs in 2-5 days for ALT, AST, and TB or 7-10 days for ALP as indicated and continue close monitoring.

^b New baseline values for DILI monitoring for ALT, AST, ALP, TB should be determined based upon average of Month 3 and Month 6 values if average is $>50\%$ decrease from original baseline. Adapted from [Palmer 2020](#).

^c Liver signs and symptoms to include: new onset severe fatigue or significant worsening of baseline fatigue; new onset severe pruritus or significant worsening on baseline pruritus; nausea, vomiting, right upper quadrant pain; fever, rash, or $>5\%$ eosinophilia; new onset of hepatic decompensation (e.g., ascites, variceal bleeding, hepatic encephalopathy).

^d Symptoms of rhabdomyolysis may include muscle swelling; weak, tender or sore muscles; dark urine; fever; tachycardia; nausea and vomiting; confusion; dehydration; or abdominal pain.

^e If IP interrupted due to CK trigger, closely monitor CK and creatinine/renal function in addition to liver biochemistries every 2 weeks until values return to baseline levels; same criteria apply to considering re-initiation of IP. CK levels should be assessed in patients reporting symptoms of rhabdomyolysis, and investigational product should be discontinued if markedly elevated CK levels (≥ 5 x ULN) occur or myopathy is diagnosed.

It should be noted that it is difficult to recognize every potential marker of hepatic deterioration or muscular injury. There is no substitute for good medical judgment. Investigators will be reminded to be cautious and mindful in their evaluation of subjects' symptoms, signs, and laboratory results. However, for example, a single abnormal laboratory analyte result may be artifactual; accordingly, Investigators will be allowed to implement an alternate follow-up procedure if considered appropriate based on their medical judgement but only after documented agreement with the Sponsor's Medical Monitor.

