10.3. Clinical Laboratory Evaluations

Laboratory parameters will be summarized in both conventional and standard international system of units using descriptive statistics at Baseline and at each on-study evaluation. Baseline is defined as the mean of all available evaluations prior to the first administration of investigational product.

The normal ranges of the selected lab parameters are defined below. The abnormal indicators of the selected lab parameters will be derived based on these normal ranges (inclusively):

- ALP 44-122 U/L
- ALT 0-45 U/L
- AST 0-45 IU/L
- GGT 0-65 IU/L (male) 0-60 IU/L (female)
- Total Bilirubin 1.71-12.3 umol/L
- Direct Bilirubin 0-0.4 mg/dL
- Cholesterol 0-169 mg/dL (age ≤19), 0-199 mg/dL (age >19)
- LDL 0-109 mg/dL (age ≤19), 0-99 mg/dL (age >19)
- HDL >39 mg/dL
- Creatinine 0.57-1.27 mg/dL
- Creatine 0.0-0.7 mg/dL (male) 0.1-1.0 mg/dL (female)
- CK 41-439 U/L (male, age 18-50 years old), 41-331 U/L (male, age 51-80 years old),

32-182 (female, age 18-80 years old)

For the other lab parameters, the normal ranges and abnormal indicators are based on the values in the data from the central or local labs.

In addition, shift tables (i.e., low-normal-high at Baseline versus low-normal-high at post-Baseline visit in a 3-by-3 contingency table) from Baseline to worst value, last value, and at each scheduled post Baseline visit will be provided for hematology and serum chemistry to assess changes in laboratory values from Baseline to each on-study evaluation from the central or local labs. The subjects meeting Hy's law criteria (defined as AST or ALT ≥ 3 xULN together with total bilirubin ≥ 2 xULN at any timepoint) will be summarized by visit.

Urine chemistry and urinalysis results will not be summarized but will be provided in a data listing.

All clinical laboratory data (including central and local) will be presented in by-subject data listings.

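### SAP 5.5 limits analyses to scheduled visits, which conflicts with the any-time Hy's law and worst-value tables in SAP 10.3, and nothing says which rule governs

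*SAP*

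**What the plan says.** - **SAP 5.5 (Analysis Windows).** No windows are defined. "Only the scheduled visits will be included in the analyses"; "All visits, including unscheduled visits, will be presented in the listings". No output is exempted.
- **SAP 10.3 (Clinical Laboratory Evaluations), shift tables.** Shifts run "from Baseline to worst value, last value, and at each scheduled post Baseline visit will be provided for hematology and serum chemistry", using central or local laboratory values.
- **SAP 10.3, Hy's law.** Subjects with AST or ALT at least 3 times ULN and total bilirubin at least 2 times ULN "at any timepoint) will be summarized by visit".
- **SAP 10.3, normal ranges.** Fixed ranges are written in for a named set of analytes that includes ALP, ALT, AST, GGT, bilirubin, creatinine and CK. Only the remaining analytes take the range supplied by the central or local laboratory.
- **Protocol 15.3 (Safety Analysis).** The laboratory summary, with Hy's law named in it, is given at baseline and at scheduled post-baseline visits.
- **Protocol 7.4.2 and Table 4.** Signs or symptoms of liver or muscle injury, or a laboratory alert, lead to unscheduled visits. Footnote a of Table 4 asks for "close monitoring (repeat labs and exam 2-3 times per week"; footnote e has CK repeated every 2 weeks after a CK trigger. If the subject cannot attend a visit, or an immediate assessment is needed, "the use of a local lab is permissible at the discretion of the Investigator", and the investigator then obtains that laboratory's normal ranges.

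**The concern.** Long-term safety is the primary objective, and the Hy's law and worst-value tables are the laboratory displays most likely to be read for a liver or muscle signal. Both are meant to show extremes. In this protocol an extreme will often be recorded at an unscheduled visit, because a suspected injury is what triggers the extra testing. A rule that keeps unscheduled results out of every table therefore removes data because an event is suspected, and the resulting bias is towards no signal.

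SAP 10.3 appears to intend something wider than SAP 5.5 allows. Two programmers working from the same SAP could produce different Hy's law and worst-value counts from the same data. In an open-label study, that choice should not be left until results are visible.

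**Working it through.** The plan states no figure on this point, so there is none to reproduce. The check has three parts.

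**1. The texts side by side**

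| Output | Under SAP 5.5 | As worded in SAP 10.3 | Protocol |
|---|---|---|---|
| By-visit summaries and changes | Scheduled visits | Each on-study evaluation | Scheduled visits (15.3) |
| Worst- and last-value shifts | Scheduled visits | Named separately from scheduled visits; central or local | Each evaluation through Month 60 or ET (15.3.2) |
| Hy's law | Scheduled visits | Met at any time, displayed by visit | Scheduled visits (15.3) |

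If worst value meant only the worst scheduled value, 10.3 could still be read consistently with 5.5. The any-time wording for Hy's law is harder to square with it. Protocol 15.3 favours the 5.5 reading. No sentence settles the matter. CK belongs to serum chemistry in protocol Table 11, so the same question applies to the CK shifts.

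**2. How often a scheduled draw would catch a short episode**

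Inputs from the documents:
- Scheduled post-baseline laboratory visits fall at Months 1, 3, 6 and 12 and then every 6 months to Month 60, which is 12 visits (protocol 7.1.1 and Table 3).
- From Month 6 the gap is 6 months, for 60 − 6 = 54 of the 60 months. In days the gap is 365.25/2 = 182.6.
- After a Table 4 trigger, laboratory tests are repeated 2 to 3 times a week, with at least 30 days before any restart (footnote a).

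Assumptions not in the documents: the episode lasts *d* days, and its onset is uniform within the gap. Then P(episode spans a scheduled draw) = *d*/182.6.

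| Assumed duration | Calculation | Probability |
|---|---|---|
| 14 days | 14/182.6 | 8% |
| 30 days | 30/182.6 | 16% |
| 60 days | 60/182.6 | 33% |
| 90 days | 90/182.6 | 49% |

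Between Months 3 and 6 the gap is 91.3 days, and the 30-day figure rises to 30/91.3 = 33%.

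If the stated repeat frequency continues through a 30-day interruption, it yields 2 × 30/7 = 8.6 to 3 × 30/7 = 12.9 draws, so about 9 to 13 unscheduled results against 0 or 1 scheduled ones.

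**3. Which range is applied**

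Protocol 7.4.2 has sites obtain local normal ranges. SAP 10.3 uses laboratory-supplied ranges only for analytes outside its fixed list. For ALT, AST, ALP, bilirubin, creatinine and CK, the fixed ranges therefore override the local ones when results are flagged as abnormal. SAP 10.3 does not say separately which ULN serves Hy's law. The fixed ranges are the only ones it gives for those analytes.

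**The case against.** The strongest reply is that SAP 10.3 is the section specific to laboratory data and should prevail over a general rule. It names worst and last value apart from scheduled visits, and it defines Hy's law at any time. This stands to the extent that exclusion cannot be called settled. It does not remove the problem, because 5.5 has no exception and protocol 15.3 points the other way.

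The second reply is that little would be hidden. Under protocol 14.2.6, clinically significant laboratory changes, as judged by the investigator, are recorded as adverse events, and needing discontinuation or closer follow-up counts towards significance. Such events reach the TEAE tables and, where the term qualifies, the hepatic injury table in SAP 10.2.4. Potential hepatic injury is adjudicated (protocol 14.3), the DMC sees laboratory and hepatic adjudication results (protocol 15.9), and every result is listed. This is a real offset, but a partial one. It depends on investigator judgement and on coding. The myalgia table in SAP 10.2.4.2 takes a single preferred term and would not show a CK rise coded otherwise. The visible text of SAP section 10 describes no table of adjudicated hepatic injury.

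Four stronger readings are tempting, and the documents do not support them:

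- **That local-laboratory results are dropped as such.** SAP 10.3 includes them in the shift tables, and a local laboratory may serve a scheduled visit. Only local results from unscheduled visits are in question.
- **That early termination results belong to no table.** ET is a named column in protocol Table 3, and protocol 15.3.2 carries shifts through Month 60 or ET.
- **That the complement of the percentages above (84% for 30 days) is the share of episodes lost through SAP 5.5.** The durations are assumed. Onset is not random for episodes first found at a scheduled draw, although a later peak could still fall outside one. An episode that prompts no test is never measured, and no SAP wording recovers it.
- **That the range "Total Bilirubin 1.71-12.3 umol/L" has a wrong upper limit.** By the protocol's conversion (51.3/3 = 17.1), 12.3/17.1 = 0.72 mg/dL, which may look low. The central laboratory's range is not in the documents, so no error is shown. A low ULN would also raise Hy's law counts, since 2 × 12.3 = 24.6 µmol/L is easier to exceed.

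**Conclusion.** The point holds as an unresolved conflict. SAP 5.5 and protocol 15.3 point to scheduled visits only, SAP 10.3 points to all results for Hy's law and worst and last value, and nothing says which governs. If 5.5 is followed literally, the Hy's law and worst-value tables leave out the results recorded while a suspected liver or muscle injury is being worked up, and they are biased towards no signal.

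The size of that bias cannot be derived from the documents. The 16% for a 30-day elevation (8% to 49% for 14 to 90 days) is an illustration. It assumes random onset, applies to the 6-monthly gaps from Month 6, and matters only if 5.5 governs. The data themselves are not lost, since listings, adverse event tables and adjudication remain.

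A smaller related point also holds: the fixed ranges in SAP 10.3 override the local ranges that sites are asked to collect for the main liver, renal and muscle analytes.

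**What to change.** 1. In SAP 5.5, limit the scheduled-visit rule to by-visit summary and change-from-baseline tables.
2. In SAP 10.3, state that Hy's law and the worst- and last-value shifts, CK included, use all results after the first dose: scheduled, unscheduled, ET, central and local.
3. Add an overall Hy's law count, each subject counted once, beside the by-visit display.
4. For local-laboratory results, apply the reporting laboratory's own normal range in place of the fixed ranges in SAP 10.3.
5. Reconcile this with protocol 15.3, or record the change in SAP section 11, which at present declares no departures from the protocol's analyses.

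The cost is SAP wording and programming. All visits and all central and local results are already due to be listed, and local ranges are already to be obtained, so no new data collection is needed. The downside for the sponsor is that safety counts may look less favourable.

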6. SUBJECT DISPOSITION

Subject disposition will be tabulated in overall and will include, as appropriate, the following number and proportion of subjects:

- LTSE population
- PK population
- Completed study
- Study discontinuation and reasons
- Investigational product discontinuation and reasons

Disposition summaries of both end of study and end of treatment will be presented for each analysis population and will be tabulated in overall.

A by-subject data listing of study completion information including the reason for premature treatment and study withdrawal, if applicable, will be presented.

6.1. Protocol Deviations

The Investigator is not permitted to deviate from the protocol in any significant way without proper notification to the Sponsor (or designee).

Major protocol deviations that could potentially affect the efficacy or safety conclusions of the study will be identified prior to database. Major protocol deviations will be summarized by deviation category using the LTSE population.

Protocol deviations will be presented in a by-subject data listing.

7. DEMOGRAPHICS AND BASELINE DISEASE CHARACTERISTICS

7.1. Demographics and Baseline Characteristics

Demographic variables will include the following:

- Age at informed consent (Continuous and Categorical (<65 and ≥65))
- Sex (Male and Female)
- Race (American Indian or Alaska Native, Asian, Black or African American, Native Hawaiian or Other Pacific Islander, White and Other)
- Ethnicity (Hispanic or Latino, Not Hispanic or Latino, Not reported)
- Geographic Region

Other Baseline characteristics will include the following:

- Weight (kg)
- Height (cm)
- BMI (kg/m²)

Key liver function test results as a continuous variable and categorized as follows:

- ALP (U/L)
- Total Bilirubin (μmol/L)
- Albumin (g/L)
- Use of UDCA (Yes/No)

- Total daily dose of UDCA (mg) as determined using the last dosage reported prior to the first dose

Demographics and Baseline characteristics will be summarized and presented in overall for LTSE and PK populations. For categorical variables, the number and percentage of subjects within each category, including a category for missing data, will be presented. For continuous variables, summary statistics will include the number of subjects and the mean, SD, SEM, median, 25th and 75th quartiles, minimum, and maximum values. No inferential statistical comparisons will be performed.

All demographic and Baseline characteristics data will be presented in by-subject data listings.

7.2. Baseline PBC Disease Characteristics

Baseline PBC disease characteristics will be summarized using data collected from the PBC Disease History and other eCRFs. Variables of the PBC Disease History include the following:

- Age at PBC diagnosis
- Duration of PBC in years at time of informed consent
- History of PBC related pruritus (Yes/No)
- Severity of most recent pruritus event
 - Ongoing at screening
- History of PBC-related fatigue (Yes/No)
 - Ongoing at screening
- Overall severity of PBC-related fatigue

Baseline PBC disease characteristics will be summarized and presented in overall for LTSE population.

Baseline PBC disease characteristics will be presented in by-subject data listings.

8. MEDICAL HISTORY

Verbatim terms on eCRFs will be mapped to preferred terms and system organ classes using the Medical Dictionary for Regulatory Activities (MedDRA).

Medical history will be summarized by system organ class, preferred term using the LTSE population. Summaries will be ordered by descending order of incidence of system organ class and preferred term within each system organ class.

Medical history will be presented in a by-subject data listing.

9. EFFICACY ANALYSES

The efficacy endpoints of the study are defined below. Additionally, the planned analyses for these endpoints are described. All efficacy endpoints will be presented in by-subject data listings.

Missing data will be assumed to be missing at random. In order to determine the effect of missing data on the analysis, efficacy endpoints will be analyzed using different methods of imputation as described below.

During the conduct of the study, the DMC may recommend refining the missing data strategy to better address the observed pattern of missing data, based on blinded monitoring of the data.

All efficacy analyses will be summarized using descriptive statistics at Baseline and at each scheduled postbaseline visit. The change from baseline and percent change from baseline will also be summarized. Descriptive statistics, including change from baseline, percent change from baseline, and estimates of least-square (LS) means, SEs, and 95% CIs, will be presented.

Estimates of the mean difference between treatment groups, the SE of the difference, and 2-sided 95% CI of the difference will also be presented.

In efficacy analyses, subjects who do not provide an assessment at the specified timepoint for the defining of response will not be included. That is, for the percentage of responders, the subject will not be included in the numerator or the denominator.

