3. Male subjects who are sexually active with female partners of childbearing potential must agree to use a condom with spermicide and to use (or have their partner use) 1 other approved method of highly effective contraception from the initiation of the study and until at least 90 days after the last dose of investigational product as listed in Inclusion Criterion #2.
 4. Male patients must refrain from sperm donation from the initiation of the study and until at least 90 days after the last dose of investigational product.
 5. Must provide written informed consent and agree to comply with the study protocol.

Key Exclusion Criteria:

1. Any history or presence in the last 30 days, before rolling over to this study, of other concomitant liver diseases, including any of the following:
 - Hepatitis C virus (HCV) infection with positive RNA
 - Active hepatitis B virus (HBV) infection; however, subjects who have seroconverted (hepatitis B surface antigen negative [sAg-], hepatitis B surface antibody positive [sAB+]; hepatitis B e-antigen negative [eAg-], hepatitis B e-antibody positive [eAb+]; HBV DNA negative) may be included in this study after consultation with the Medical Monitor and Sponsor Medical Monitor
 - Subjects should be excluded if positive HBV DNA or HCV RNA
 - Primary sclerosing cholangitis
 - Alcoholic liver disease
 - Definite autoimmune liver disease or PBC-autoimmune hepatitis (AIH) overlap
 - Metabolic dysfunction-associated steatohepatitis (MASH)
 - Gilbert's Syndrome (due to interpretability of bilirubin levels)
 - Rare liver conditions such as Wilson's disease, hemochromatosis, alpha-one anti-trypsin deficiency, or other conditions identified by the Principal Investigator
2. Clinical complications of PBC including:
 - Prior liver transplantation
3. Any history or presence in the last 30 days, before rolling over to this study, of any one of the following decompensating events:
 - Child-Pugh (CP) Score ≥ 7

- Clinical evidence of decompensated liver disease or evidence of portal hypertension, including but not limited to:
 - Varices (including a history of esophageal varix ligation or asymptomatic esophageal varices by endoscopy)
 - Ascites/hepatic hydrothorax
 - Spontaneous bacterial peritonitis
 - Hepatic encephalopathy
 - Jaundice (with total bilirubin >3 mg/dL [$>51.3 \mu\text{mol/L}$])
 - Biochemical evidence of hepatic impairment, decompensation, or injury including at least one of the following:
 - Total bilirubin >ULN

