14.2. Other Safety Parameters

14.2.1. MELD Score

The MELD scoring system is used to assess the severity of chronic liver disease. The MELD score is useful in assessing patients with significant decompensation and the MELD score is now used by the United Network for Organ Sharing in the US and Eurotransplants to manage the organ allocation for liver transplantation. The threshold for placement on an organ transplantation queue varies between regions across the globe, but a score of 15 may result in a place on the transplant waiting list in the US.

An increasing MELD score is associated with increased severity of hepatic dysfunction and increased 3-month mortality risk. The MELD score is derived from the patient's serum total bilirubin, serum creatinine, and INR, as appropriate, to predict survival and is calculated according to the following formula ([Kamath 2007](#)):

$$\text{MELD} = 3.78 \times \ln(\text{serum bilirubin [mg/dL]}) + 11.2 \times \ln(\text{INR}) + 9.57 \times \ln(\text{serum creatinine [mg/dL]}) + 6.43$$

INR will be calculated based on PT value by the central laboratory.

MELD score will be reported in whole numbers on the eCRF according to the frequency listed in [Table 3](#).

For a MELD score ≥ 15 to be considered as an outcome endpoint, an indication of the presence of cirrhosis and the progression of liver disease must be present. However, transient increases of total bilirubin, creatinine, or INR values due to causes other than progression of liver disease should be ruled out (e.g. use of medications that may cause an increase in INR). In addition, it should be ascertained by the adjudicators that the change in MELD score is sustained and not transient. Additionally, the subject must have MELD ≤ 12 at baseline (defined as the last assessment performed before the first dose of investigational product in Study 977-311).

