5.4. Calculations

Variables requiring calculation will be derived using the following formulas:

- Days – A duration expressed in days between one date (*date1*) and another later date (*date2*) will be calculated using the following formulas:
$$\text{duration in days} = \text{date2} - \text{date1} + 1, \text{ where } \text{date1} \geq \text{first dose date}$$
$$\text{duration in days} = \text{date2} - \text{date1}, \text{ where } \text{date1} < \text{first dose date}$$
- Months – A duration expressed in months is calculated as the number of days divided by 365.25/12 (approximately 30.4)
- Years – A duration expressed in years between one date (*date1*) and another date (*date2*) is calculated using the following formulas:

duration in years= (date2 – date1 + 1)/365.25, where date1 ≥first dose date

duration in years= (date2 – date1)/365.25, where date1 <first dose date

- Age of diagnosis – Age of diagnosis is calculated as the number of years from the imputed year of birth (*DOB*) to the year of diagnosis. The imputed year of birth is derived as year of inform consent – age. The following formula is used:

age (years)= year of diagnosis – imputed year of DOB + 1

- Height – Height entries made in inches are converted to centimeters using the following formula:

height (cm)= height (in) × 2.54

- Weight – Weight entries made in pounds are converted to kilograms using the following formula:

weight (kg)= weight (lb) / 2.2046

- Temperature – Temperature entries in degrees Fahrenheit are converted to degrees Celsius using the following formula:

temp (degrees Celsius) =5 / 9 × (temp [degrees Fahrenheit] – 32)

- Body Mass Index (BMI) – BMI is calculated using height (cm) and weight (kg) using the following formula:

[figure not shown]
BMI (kg/m²) =weight (kg) / ([height (cm)/100]²)

- Change from Baseline – Change from Baseline will be calculated as:

Change=post Baseline value – Baseline value

- Percentage change from Baseline – Percentage change from Baseline will be calculated as:

Percentage change from Baseline= ([post Baseline value – Baseline value] / Baseline value) × 100

Note: TRANS= ALT ratio to upper limit. When ALT is missing, TRANS=AST ratio to upper limit.

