9.1. Efficacy Endpoints

The LTSE Population will be the population used for the efficacy analyses. Baseline is defined as the last assessment performed before the first dose of investigational product in Study 977-311, unless otherwise specified.

The efficacy endpoint at post-baseline site visits includes:

- Response rate of $\geq 40\%$ reduction from baseline and normalization rates of ALP
- Normalization rates of GGT, ALT, AST, total and conjugated bilirubin
- Change from baseline in GGT, ALT, ALP, AST, and total and conjugated bilirubin
- Percentage of subjects with ALP $< 1.67 \times \text{ULN}$, total bilirubin $\leq \text{ULN}$, and ALP decrease of $\geq 15\%$ from baseline
- Change from baseline in noninvasive markers of liver fibrosis, including liver stiffness measured by TE and ELF score
- Change from baseline in the GLOBE, UK-PBC, and MELD scores

All continuous and categorical additional endpoints will be summarized using descriptive statistics at baseline and at each scheduled post-baseline visit. No statistical inference will be done on those endpoints.

[figure not shown]
The intercurrent event in this study includes the use of prohibited medication and treatment discontinuation. Data collected after the intercurrent events, such as the use of prohibited medications, and data collected after treatment discontinuation will be included in the analyses (Treatment Policy Estimand).

The 5 attributes of the efficacy estimand are provided in Table 1.

[figure not shown]
Table 1: Attributes of Efficacy Estimand

[figure not shown]
Estimand Attribute	Elements
Population	All subjects with PBC who participated and are actively taking investigational product in Study 747-213 or Study 747-214 (or other Sponsor studies)
Treatment	OCA+BZF FDC Tablets
Efficacy Endpoint	All efficacy endpoints
Intercurrent Events	Use of Prohibited medication (Treatment Policy) Treatment Discontinuation (Treatment Policy)
Primary Efficacy Endpoint Population Level Summary	Descriptive summary in the target population

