9.2.1.1. Child-Pugh

The Child-Pugh score (CPS) is calculated within EDC by adding the scores of the 5 factors and can range from 5-15. Child-Pugh class is either A (a score of 5-6), B (7-9), or C (10 or above). Each of the factors is outlined in Table 2.

Table 2: Child-Pugh Score

Factor	Units	Points		
		1	2	3
Serum bilirubin	μmol/L	<34	34-50	>50
	mg/dL	<2.0	2.0-3.0	>3.0
Serum albumin	g/L	>35	35-28	<28
	g/dL	>3.5	3.5-2.8	<2.8
Prothrombin time	Seconds prolonged	0-3	4-6	>6
	INR	<1.7	1.7-2.3	>2.3
Ascites		None	Mild	Moderate-Severe
Hepatic encephalopathy		No	Grade 1 or 2	Grade 3 or 4

The ascites and hepatic encephalopathy variables are based on the investigator's clinical assessment.

The CP score will be summarized in the same manner as described above for the MELD score.

Child-Pugh class will be presented in shift tables showing the shift from baseline to each scheduled post-baseline visit by the count and percentage of subjects within each shift classification.

Individual factors will be presented in a listing.

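### SAP 9 asks for percent change from baseline in MELD, which under the protocol's formula can be zero or negative at ordinary eligible values, so the percentage is undefined or has the wrong sign

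*SAP*

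**What the plan says.** SAP 9 states that every efficacy analysis is summarized descriptively at baseline and at each scheduled visit, and adds: "The change from baseline and percent change from baseline will also be summarized". The next sentence of that section names percent change again. No endpoint is exempted.

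SAP 5.4 defines the quantity as "Percentage change from Baseline= ([post Baseline value – Baseline value] / Baseline value) × 100". It has no rule for a baseline that is zero or negative.

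SAP 9.1 lists among the efficacy endpoints "Change from baseline in the GLOBE, UK-PBC, and MELD scores".

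Protocol 14.2.1 builds MELD from the logarithms of bilirubin, INR and creatinine plus a constant. It states no lower limit for any input or for the total, and adds that "MELD score will be reported in whole numbers on the eCRF".

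For eligibility, the synopsis and Protocol 8.3 exclude subjects with "Total bilirubin >ULN" in the 30 days before rollover.

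**The concern.** Percent change is informative when the baseline is a positive quantity on a scale with a true zero. MELD as written in Protocol 14.2.1 is not such a quantity: it is a log-linear index whose zero is an accident of the constant 6.43. In a population selected for normal bilirubin, the logarithmic terms are mostly negative and the score falls close to zero.

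Three things then go wrong in a MELD percent-change column. A subject with a stored baseline of 0 drops out. A subject with a negative baseline has the sign reversed, so worsening shows as a decrease. Subjects with a baseline just above zero produce very large percentages that dominate the mean.

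**Working it through.** The plan states no figure to reproduce here, so the check evaluates the protocol's formula and then applies the SAP's percent-change rule.

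**Inputs**
- Formula (Protocol 14.2.1): MELD = 3.78 ln(bilirubin) + 11.2 ln(INR) + 9.57 ln(creatinine) + 6.43, with bilirubin and creatinine in mg/dL.
- Bilirubin normal range (SAP 10.3): 1.71-12.3 µmol/L. The protocol equates 3 mg/dL with 51.3 µmol/L, a factor of 17.1, so the range is 0.10-0.72 mg/dL.
- Creatinine normal range (SAP 10.3): 0.57-1.27 mg/dL.
- INR: no normal range is given; 0.9-1.1 is assumed.
- Rounding: to the nearest whole number, halves up (SAP 5.3).

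**Step 1: the bilirubin term.** At the SAP's upper limit it is 3.78 × ln(0.72) ≈ -1.25. It is therefore negative for anyone at or below that limit.

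**Step 2: single subjects at INR 1.0, where the INR term is 0**

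| Bilirubin | Creatinine | Calculation | MELD | Stored |
|---|---|---|---|---|
| 0.50 | 0.70 | -2.62 - 3.41 + 6.43 | 0.40 | 0 |
| 0.40 | 0.70 | -3.46 - 3.41 + 6.43 | -0.45 | 0 |
| 0.35 | 0.65 | -3.97 - 4.12 + 6.43 | -1.66 | -2 |
| 0.60 | 0.70 | -1.93 - 3.41 + 6.43 | 1.09 | 1 |

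**Step 3: apply SAP 5.4**
- Rows 1 and 2: the divisor is 0, so percent change is undefined.
- Moving from row 3 to row 4 is a worsening of 3 points. Percent change = (1 - (-2)) / (-2) × 100 = -150%.
- Without rounding the problem remains. At creatinine 0.65, bilirubin rising from 0.4 to 0.6 takes MELD from -1.16 to +0.38, and percent change is -133%.
- Near zero, unrounded: 0.40 to 1.75 is a change of 1.35 points and prints as +340%.

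**Step 4: where the boundary lies.** At INR 1.0 the stored score is 0 or less when bilirubin is at or below about 0.76 mg/dL (creatinine 0.6), 0.51 (0.7), 0.37 (0.8) or 0.27 (0.9).

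**Step 5: how often.** The documents give no baseline distributions, so this step is assumption-based.
- Bilirubin and creatinine independent and uniform over the SAP normal ranges: stored MELD is 0 or less in 50% at INR 0.9, 36% at INR 1.0 and 24% at INR 1.1. It is exactly 0 in 8-12%.
- Log-normal inputs, bilirubin truncated at 0.72 mg/dL, assumed log-SDs of 0.35 (bilirubin), 0.15 (creatinine) and 0.05 (INR):

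| Median bilirubin | Median creatinine | Median INR | Stored MELD 0 or less | Of 133 |
|---|---|---|---|---|
| 0.35 | 0.65 | 0.95 | 92% | 123 |
| 0.45 | 0.75 | 1.00 | 51% | 68 |
| 0.55 | 0.90 | 1.05 | 7% | 10 |

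Raising the creatinine log-SD to 0.18 changes these shares to about 90%, 51% and 10%.

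**The case against.** The strongest objection is that the deciding SAP text cannot be seen. SAP 9.2.1.1 says "The CP score will be summarized in the same manner as described above for the MELD score", but no MELD description precedes it in the public text. The SAP's abbreviation list also defines OPTN and Na, which the visible text never uses, so a separate MELD derivation may exist. If it raises inputs below 1 to 1, a subject with normal bilirubin and with INR and creatinine at or below 1 scores 6.43, stored as 6, and percent change is defined and correctly signed. This stands as a limit on the point. It would also mean that the SAP and Protocol 14.2.1 compute different scores.

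A second objection is that SAP 9.1 and Protocol 15.4 name only change from baseline for MELD, and that the percent-change sentence is generic. That is fair, but the ALP and GGT bullet is worded the same way, so the bullet's wording does not exempt MELD.

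Three stronger readings are tempting and are not supported:
- *That a known share of subjects is affected.* No baseline data are given, and the scenarios run from 7% to 92%. The bilirubin limit also did not bind everyone: the first subject enrolled in July 2024, and Version 2.0 of 18 November 2024 lowered the exclusion from above 3 mg/dL to above ULN (Protocol Appendix B).
- *That the same error affects Child-Pugh, ELF, GLOBE and UK-PBC.* Child-Pugh cannot fall below 5, so its percent change is always defined and correctly signed. No zero or negative baseline is shown for the others, and the GLOBE and UK-PBC formulas are not in the public text.
- *That deterioration would pass as improvement in the study's conclusions.* The study tests no hypothesis, its primary objective is safety, and correctly signed absolute change and by-subject listings are produced as well. The MELD ≥15 outcome uses an absolute threshold.

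**Conclusion.** The point holds for MELD. Taken as written, SAP 9 and SAP 5.4 combined with Protocol 14.2.1 give an undefined or sign-reversed percentage for ordinary eligible laboratory values. The worked examples need no distributional assumption. The frequency does: about 24-50% under uniform values over the SAP normal ranges with INR 0.9-1.1, and about 7-92% across the log-normal scenarios.

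The conclusion assumes that the analysis uses the protocol's formula without input floors, which the public SAP text neither confirms nor rules out. The consequence is modest: one misleading descriptive column, with no effect on the primary safety objective.

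**What to change.** In SAP 9, state that MELD is summarized by observed value and absolute change from baseline only, with no percent change. Absolute change is defined for every subject with both values, and Protocol 15.4 does not ask for percent change in MELD, so nothing required is lost.

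In the same edit, confirm that the SAP and Protocol 14.2.1 use one MELD derivation, and state any lower bounds on the inputs in both documents.

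Dropping percent change for Child-Pugh, ELF, GLOBE and UK-PBC is optional; it is a matter of interpretability and is not shown to correct an error.

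The cost is a sentence or two in the SAP and fewer table columns, plus a protocol clarification if the derivations differ. No data collection changes.
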